PK	pharmacokinetic(s)
PMM	pattern-mixture model
PP	Per Protocol
PRO	patient-reported outcome
PT	Preferred Term
QTcF	Fridericia corrected QT interval
SAP	statistical analysis plan
SAE	serious adverse event
SD	standard deviation
SE	standard error
SOC	System Organ Class
SSR	sample size reestimation
TEAE	treatment-emergent adverse event
TFL	tables, figures, and listings
T1DM	type 1 diabetes mellitus
T2DM	type 2 diabetes mellitus
WHO	World Health Organization

CONFIDENTIAL

Document Date: 07JUN2022

Page 6 of 55
ST-AD-008 version 05

1. Source Documents

The Statistical Analysis Plan (SAP) was written based on the following documentation:

Document	Date	Version
Protocol	05 December 2019	Final
Protocol Amendment	17 March 2020	1
Protocol Amendment	28 August 2020	2
Protocol Amendment	09 October 2020	2.0.1
Protocol Amendment	18 November 2020	3
Protocol Amendment	09 September 2021	4
eCRF	30 September 2020	3

2. Protocol Details

2.1 Study Objectives

2.1.1 Primary Objective

The primary objective of this study is to evaluate the efficacy of LX9211 in reducing pain related to diabetic peripheral neuropathy (DPN).

2.1.2 Secondary Objective(s)

The secondary objective of this study is to assess other effects and patient reported outcomes of LX9211 versus placebo following the 6-week double-blind Treatment Period.

2.1.3 Other Objective(s)

Other objectives of this study are:

- Change from Baseline in the Neuropathic Pain Symptom Inventory (NPSI) and to each week in the average daily pain score (ADPS), based on Question 5 of the Brief Pain Inventory – DPN (BPI-DPN).
- To evaluate plasma C_{trough} levels of LX9211 at 2 oral dose levels in patients with type 1 diabetes mellitus (T1DM) and/or type 2 diabetes mellitus (T2DM) with chronic diabetic peripheral neuropathy pain (DPNP) over a 6-week period.

The full pharmacokinetic (PK) profile of LX9211 will be evaluated in an optional substudy conducted in patients who consent to intensive PK sampling over the course of the treatment period.

Safety will be assessed by adverse events (AEs), vital signs, electrocardiogram (ECG) findings, and laboratory parameters.

2.2 Overall Study Design

This is a Phase 2, multicenter, randomized, double-blind, placebo-controlled, parallel-group study in patients with DPNP. Up to 282 patients are expected to enroll in this study.

Scheduled study visits in the clinic will occur during Screening; at the initiation of the 2-week single-blind placebo Run-in Period; on Day 1 (Baseline) and during Weeks 2, 4, and 6 of the double-blind Treatment Period, and Week 11 of the single-blind Safety Follow-up Period.

Male and female patients of age 18 years and above, diagnosed with T1DM or T2DM and with chronic DPNP, and who meet all inclusion and no exclusion criteria are eligible for enrollment.

Eligible patients may continue use of 1 medication prescribed for DPNP including pregabalin, gabapentin, and antidepressant medications, as long as they have been at stable doses for at least 1 month prior to screening and are willing to maintain their doses for the duration of the study. Use of any opioid medications for the management of DPNP within the 2 months prior to Screening is not permitted.

Screening Period: After signing the Informed Consent Form (ICF), all patients will enter a Screening Period of up to 2 weeks. Following confirmation of eligibility criteria, patients will enter the following study periods:

Run-in Period: After meeting Screening eligibility criteria, patients will enter a 2-week single-blind Run-in Period. On Day 1 of the Run-in period, patients will be administered 4 tablets of single blind study drug at the site. For the remainder of the Run-in Period, patients will take a single tablet of study drug in the morning. Each evening patients will rate and record the intensity of their DPNP over the previous 24 hours based on Question 5 of the BPI-DPN by answering the question "Please rate your pain due to your diabetes by indicating the one number that best describes your pain on the average." (0 [no pain] to 10 [pain as bad as you can imagine]) in their daily pain diary and will rate the interference of pain with sleep by completing Question 9F of the BPI-DPN. The ADPS will be calculated using all available daily pain diary data. In order to qualify for randomization, patients must

CONFIDENTIAL

complete $\geq 70\%$ of the daily pain diary entries during the week prior to randomization, meet criteria for moderate to severe pain, and demonstrate $\geq 80\%$ compliance with taking the expected amount of placebo tablets during the Run-in Period. During the Run-in Period patients will not be allowed to use any rescue medication. On the morning of the Run-in Visit, patients may consume a light meal prior to the visit.

Note: Patients who fail Screening may be rescreened ONCE after discussion with the Medical Monitor.

Randomization/Double-blind Treatment Period: Patients who successfully complete the 2-week single-blind placebo Run-in Period and meet all other eligibility criteria will enter a 6-week double-blind Treatment Period.

Patients will be randomly assigned in a 1:1:1 ratio among the following 3 treatment groups:

- **Group 1:** LX9211 100 mg* / 10 mg**, once daily (qd)
- **Group 2:** LX9211 200 mg* / 20 mg**, qd
- **Group 3:** Placebo, qd

* Loading dose (Day 1)

** Maintenance dose (Day 2 – Week 6 Visit)

Implementation of the treatment randomization schedule will be centralized. A 1:1:1 ratio for assigning patients among the treatment groups will be accomplished by use of randomly permuted blocks of fixed size.

On Day 1, patients will receive 1 of 2 dose levels of LX9211 or placebo, based on their treatment assignment, to be given as a loading dose at the clinic. Patients will remain at the clinic for observation for 2 hours following dosing. At 2 hours ± 10 minutes, orthostatic vital signs will be obtained (heart rate and blood pressure) after which time patients may be released. The loading dose will be followed by a daily maintenance dose taken at home on Day 2 through the Week 6 Visit. **Note:** On days of the clinic visits, patients will refrain from taking their daily dose until after the visit.

Each evening during the double-blind Treatment Period, patients will be required to rate and record the severity of their DPNP over the previous 24 hours based on Question 5 of the BPI-DPN by answering the question "Please rate your pain due to your diabetes by indicating the one number that best describes your pain on the average." (0 [no pain] to 10 [pain as bad as you can imagine]), record the use of rescue medication (acetaminophen), and rate the interference of the patient's pain with sleep based on Question 9F of the BPI-DPN. The ADPS will be calculated using

CONFIDENTIAL

Document Date: 07JUN2022

Page 9 of 55

ST-AD-008 version 05

all available data, however a minimum of 4 days (consecutive or non-consecutive) from the last week prior to each clinic visit is required for the calculation of weekly averages.

On the day of randomization, patients will also receive a bottle of acetaminophen. If a patient is unable to tolerate their DPNP, they are encouraged to discuss treatment options with the Investigator. At the Investigator's direction, the patient may be permitted to take acetaminophen (up to a maximum of 3 grams per day) as a rescue medication. If rescue medication does not provide adequate pain relief, the patient may discontinue from further participation in the study after consultation with the Investigator. Patients discontinuing the study prior to completion of the Week 6 Visit should also complete the Safety Follow-up Visit 5 weeks later.

Safety Follow-up Period: Following completion of the 6-week double-blind Treatment Period, all patients will enter the 5-week single-blind Safety Follow-up Period and take 1 tablet of single-blind study drug each morning during this period. During the 5-week single-blind Safety Follow-up Period, patients are allowed use of rescue medication (acetaminophen) if needed. Each evening patients will continue to rate and record the average severity of their DPNP over the previous 24 hours using Question 5 of the BPI-DPN and record the use of rescue medication (acetaminophen).

Blood samples for the determination of plasma LX9211 trough levels (C_{trough}) will be collected predose on Day 1, and at Weeks 2, 4, and 6 clinic visits, just prior to the dosing of study drug on the day of the visit. At the Week 11 EOT/EW Visit, a final sample will be collected.

Optional Substudies: During the Screening Visit, patients may choose to participate in 1 or both of 2 optional substudies.

The first substudy will include approximately 30 patients for intensive blood sampling for determination of LX9211 plasma concentrations to allow for PK parameter estimation, and additional samples for possible biomarker analyses. The PK intensive sampling will occur on Days 1 and 2 and at the Week 6 clinic visit. These patients will be confined to a clinical research unit (CRU) twice during the study for intensive PK evaluation and biomarker evaluation: prior to and following the first dose of study drug and prior to and following their final dose of study drug (planned for Week 6).

The second optional substudy is a qualitative patient interview, which will include 60 to 85 patients. The interview will be conducted over the telephone and is designed to gain insight and understanding of patients' experiences with symptoms

[figure not shown]
Statistical Analysis Plan Final v3.0

Lexicon Pharmaceuticals, Inc.
Protocol ID: LX9211.1.201-DPN

Labcorp Study ID: 000000198624

of DPNP and to assess the relevance and clinical meaningfulness of symptom improvements (eg, reduction in pain) with LX9211 treatment.

The study design is presented in the diagram below:

2.3 Sample Size and Power

A sample size of 75 patients per treatment group who complete the 6-week double-blind Treatment Period will yield 80% power to detect a true mean difference of 1 unit between at least 1 of LX9211 treatment groups and placebo in ADPS change from Baseline, assuming a common standard deviation of 2 and an overall significance level of $\alpha=0.05$ (2-sided Dunnett's test). Accounting for a dropout rate of 20%, a total of 282 patients (94 patients per treatment group; 75 patients $\times 1/(1-0.20)$) will be enrolled and randomly assigned to treatment in a 1:1:1 ratio. This sample size is adjusted for the multiple comparisons of each LX9211 treatment group with placebo ([Westfall, 1999](#)).

Sample Size Reestimation

Due to the uncertainty in the outcome for the primary endpoint analysis secondary to potential variations in some of the key design parameters such as the dropout rate and standard deviation associated with the targeted treatment group

CONFIDENTIAL

Document Date: 07JUN2022

Page 11 of 55

ST-AD-008 version 05

difference, an unblinded SSR adaptation will be implemented at the time of the interim analysis testing for futility. This will occur when the first 141 patients have been accrued and followed thru Week 6 or dropped out early from the trial (whichever event happens first). Should a patient drop out early in the study, but return for the Week 6 visit, the Week 6 data will be used in the analysis. The Chen-DeMets-Lan method will be used for the unblinded SSR since it requires minimal change from a group sequential test. This method requires specification for a number of criteria related to the allowable conditions for increasing the sample size that ensures that ordinary group sequential methods can be applied while seeing that the overall error is not inflated compared to the original group sequential design. The two primary conditions which are required and satisfied in the SSR for this study are that (a) the SSR is made at the penultimate look, and (b) the conditional power at the penultimate look occurs between 50% and 80.3% (the original specified power under the group sequential design). The SSR is linked to the projected effect size falling within this "promising" or "favorable" range of conditional power. Having satisfied these 2 main conditions, the Type I error rate after increasing the sample size until the conditional power equals the original target power will not be greater than the Type I error from the originally proposed design.

To derive the reestimated number of patients at the interim analysis, a simulation will be made that inputs: the observed group mean difference and its common standard deviation, a value for the maximum total number of patients ($E[\text{Max}]$) equal to 351 patients and, specification that the reestimation rule is the Exact E method. The Exact E method increases the patient number total until the desired conditional power is achieved.

nQuery Advisor Advanced Pro software (v8.5.2.0) (Statsols, Rathmaculling West, Cork, Ireland) was used to estimate the sample sizes.

3. Efficacy and Safety Variables

3.1 Primary Efficacy Endpoint

The primary efficacy endpoint is the change from Baseline (Week 2 of the Run-in Period) to Week 6 in ADPS, based on Question 5 of the Brief Pain Inventory - DPN (BPI-DPN), the 11-point scale (0 [no pain] to 10 [pain as bad as you can imagine]).

3.2 Secondary Efficacy Endpoints

The secondary efficacy endpoints are to be assessed in each LX9211 dose group versus placebo comparison for each of the following variables listed below:

- Proportion of patients with $\geq 30\%$ reduction in pain intensity in ADPS based on Question 5 of the Brief Pain Inventory - DPN (BPI-DPN) from Baseline to Week 6
- Proportion of patients with $\geq 50\%$ reduction in pain intensity in ADPS based on Question 5 of the Brief Pain Inventory - DPN (BPI-DPN) from Baseline to Week 6
- Change from Baseline to Week 6 in the severity of pain and interference of pain with sleep and other aspects of the patient's life based on the Brief Pain Inventory (BPI) Short Form for diabetic peripheral neuropathy (BPI-DPN) including the following:
 - Pain at its worst
 - Pain at its least
 - Pain right now
 - Interference score averaged over Questions 9A-G
 - General activity
 - Mood
 - Walking ability
 - Normal work
 - Relations with other people
 - Sleep
 - Enjoyment of life
- Proportion of patients discontinuing treatment due to lack of efficacy defined as increase in ADPS based on Question 5 of the Brief Pain Inventory - DPN (BPI-DPN) from Baseline of 30%
- Patient Global Impression of Change (PGIC) at Week 6
- Time to loss of efficacy from Week 6 to Week 11 among patients achieving at least 30% reduction in pain intensity in ADPS based on Question 5 of the Brief Pain Inventory - DPN (BPI-DPN) at Week 6

3.3 Other Efficacy Endpoints

The other efficacy endpoints are to be assessed in each LX9211 dose group versus placebo comparison for each of the following variables listed below:

- Change from Baseline to Week 6 in the NPSI
- Change from Baseline to each week in ADPS, based on Question 5 of the BPI-DPN
- Proportion of patients with $\geq 30\%$ reduction from Baseline, based on Question 5 of the BPI-DPN by week
- Proportion of patients with $\geq 50\%$ reduction from Baseline, based on Question 5 of the BPI-DPN by week

- Cumulative percentage of percent change in ADPS based on Question 5 of the BPI-DPN from Baseline to Week 6 comparing each LX9211 treatment group to placebo
- Cumulative percentage of percent change in ADPS based on Question 5 of the BPI-DPN from Week 6 to Week 11 comparing each LX9211 treatment group to placebo

3.4 Safety Variables

Safety endpoints are as follows:

- Incidence of treatment-emergent adverse events (TEAEs), suspected adverse reaction, AEs leading to discontinuation from the study, serious adverse events (SAEs), and deaths
- Actual and change from Baseline in clinical laboratory results
- Actual and change from Baseline in vital signs results, including weight
- Clinically significant change from Baseline in physical examination (PE) findings
- Actual and change from Baseline in ECG findings

4. Pharmacokinetic (PK) Variables

PK endpoints from the optional PK substudy may include, but are not limited to:

- AUC_{0-24}
- $AUC_{0-t_{last}}$
- $AUC_{0-\infty}$
- AUC_{0-T}
- CL/F
- $CL/F/kg$
- C_{max}
- C_{ss}
- t_{max}
- $t_{1/2}$
- Vz/F
- λz

Biomarker samples will be collected for patients participating in the PK substudy.

5. Analysis Populations

Analysis of the primary and secondary efficacy endpoints will be based on the Modified Intent-to-Treat (mITT) population. Safety endpoints analyses will be based on the Safety population.

5.1 Intent-to-Treat (ITT) Population

The ITT population will include all randomized patients.

5.2 Modified Intent-to-treat (mITT) Population

The mITT population will include all randomized patients who take at least 1 dose of study drug. mITT patients will be analyzed according to their randomized treatment.

5.3 Per Protocol (PP) Population

The PP population will include patients in the mITT population who complete treatment through the primary assessment of the first 6 weeks, and did not have any important protocol deviations that would interfere with the collection or interpretation of the efficacy data.

Protocol deviations are defined as any change, divergence, or departure from the study design or procedures defined in the study protocol. Important protocol deviations are a subset of protocol deviations and may significantly impact the correctness, accuracy, and/or reliability of the study data or that may significantly affect a subject's rights, safety, or well-being. [Section 5.3.1](#) details the types of deviations.

5.3.1 Important Protocol Deviations Leading to Exclusion from the PP Population Analysis

Only those important protocol deviations considered to have a major effect on efficacy will lead to complete exclusion of the patient from the PP population. For the purposes of this study, the following criteria have been identified as important protocol deviations leading to exclusion from the PP population as it is considered that the occurrences of any of these criteria might have an important influence on the primary efficacy endpoint.

Statistical Analysis Plan Final v3.0

Type	Important Protocol Deviation Leading to Exclusion from the PP population	Method of Identification
Prohibited Medication	Patients who take medications that are not permitted during the double-blind Treatment Period	Non-programmable review of blinded prior and concomitant medications listings Labcorp will provide the Medical Monitor with the lists of prior and concomitant medications taken by patients. The Medical Monitor will review this list and note any prohibited medications or therapies within 1 month prior to the Screening Visit. Patients will be excluded if they had prohibited medications or therapies within 1 month prior to the Screening Visit.
Entry Criteria Violations	Patients did not meet Inclusion Criterion 9 which is thought to impact efficacy	Programmatic check based on eligibility data
Noncompliance During 6-week Double-blind Treatment Period	Patients who had low study drug compliance rate (<80%)	Programmatic check based on exposure and drug accountability data
Minimum Treatment Duration	Patients did not receive at least 5 weeks of double-blind treatment	Programmatic check based on the exposure data
Week 6 ADPS Missing	Patients did not have at least 4 ADPS scores within Week 6 in order to calculate weekly ADPS	Programmatic check of ADPS data
Errors in Treatment Allocation	Patients who received a wrong treatment at 1 or more study visits due to packaging or dispensing errors during the double-blind Treatment Period	Programmatic check based on unblinded IRT database after the study is unblinded. The check will be done by comparing the kit number that IRT had assigned to the patient/visit against the kit number actually used.

CONFIDENTIAL

Statistical Analysis Plan Final v3.0

Lexicon Pharmaceuticals, Inc.
Protocol ID: LX9211.1.201-DPN

Labcorp Study ID: 000000198624

Incorrect Stratum used in Randomization	Patients were randomized using an incorrect stratum	Programmatic check of IRT database compared to ADPS from Run-in
Clinical Trial Management System	Labcorp Clinical will provide the list of protocol deviations based on the clinical monitoring.	Non-programmable: The list will be reviewed prior to database lock and unblinding, and the important protocol deviations leading to exclusion from the PP population will be identified.

As defined in the table, a set of the important protocol deviations leading to exclusion from the PP population will be determined programmatically from the data. Those criteria which require clinical or medical monitoring interpretation will be reviewed prior to database lock.

All important protocol deviations occurring during the study will be reviewed and approved by Lexicon Pharmaceuticals, prior to database lock unblinding. Should additional important protocol deviations leading to exclusion from the PP population, not anticipated at the time of preparing this SAP, be identified during the study (and prior to unblinding), they will be provided in a separate document and included in all relevant protocol deviation reviews and approvals.

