7.3 Prohibited Medication

- Use of NSAIDS on chronic basis within 2 weeks prior to Screening or at any time for the duration of the study for treatment of DPNP is not permitted.
- Use of opiates in the 2 months prior to Screening or at any time for the duration of the study for treatment of DPNP is not permitted **Note:** Brief use (<1 week) of opioid medication for management of non-DPNP acute pain (eg, tooth extraction/acute injury) at least 1 month prior to the Screening Visit is permitted.
- Cannabidiol, if used for mood or sleep, is acceptable. If used for DPNP it would be
 allowed if it is the only concomitant medication being taken for DPNP. If it is not the
 only medication being taken for DPNP, it should be withdrawn at least 1 month prior to
 Screening.
- Patients may not use additional medications for DPNP other than those medications prescribed for DPNP including pregabalin, gabapentin, and antidepressant medications, which have been taken at stable doses for at least 1 month prior to Screening.

• **Note:** At the Investigator's discretion, patients may take up to 3 grams of acetaminophen per day as rescue medication for DPN pain.

Patients must not have received any investigational agent or study drug within 30 days or 5 half-lives, whichever is longer, prior to Screening or at any time for the duration of the study.

All medications, including the study drug, taken by patients during the study will be captured in the source documents and recorded on the eCRF.

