- c. A complete physical examination will include, at minimum, a review of the patient's general appearance, head, eyes, ears, nose and throat, neck, heart, lungs, abdomen, back and extremities, skin, and general neurological system. A symptom related brief physical exam will only occur if the patient is experiencing symptoms or AEs. If a symptom related brief physical exam is required, it should include a review of all body systems that relate to the symptoms and/or AE the patient is experiencing.
- d. Orthostatic vitals will be collected on the Day 1 Visit 2 hours (±10 min.) post dose of double-blind study drug.
- e. The 12- lead ECG recordings should be obtained prior to the morning study drug administration. ECG recording should be recorded either prior to phlebotomy or at least 30 minutes after phlebotomy.
- f. Concomitant medications taken from 2 weeks prior to the Screening Visit through the Week 11/EOT/EW visit will be recorded.
- g. All SAEs will be collected starting with signing informed consent and continue through the Week 11 Safety Follow-up Visit.
- The collection of AEs will start after the first dose of double-blind study drug and collection will continue through the Week 11 Safety Follow-up Visit.
- Serum pregnancy test must be performed at Screening for all females. All other required pregnancy tests can be performed via a urine test. Baseline
 urine test result must be reviewed prior to Randomization. The Investigator may perform additional tests at their discretion or as required by local
 regulations.
- j. If necessary, follicle-stimulating hormone will be measured at Screening to confirm postmenopausal status.
- k. C_{trough} blood samples will be drawn predose on Day 1 and at Weeks 2, 4, and 6, just prior to the dosing of study drug on the day of the clinic visit. At the Week 11/EOT/EW Safety Follow-up Visit, a final sample will be collected.
- Qualitative patient interviews are to be completed by an independent third-party vendor within 2 weeks following the Week 6 Visit or Early Withdrawal Visit.

14. Appendix B - Substudy of PK on Day 1, Day 2, and Week 6 Visits: Procedure Listing

Week/Visit Window (days)	Day -1	Day 1 (Baseline)	Day 2	Day prior to Week 6 Or EOT / EW	Week 6 Or EOT / EW	Week 6 + 1 Day Or EOT / EW
Check into CRU	X	or predose X		X	or predose X	
Confined to CRU		X	8		X	
Discharge from CRU		-	X			X

PK Sample Collection Times on Day 1, Day 2 (predose), and Week 6 Visits

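### The per-protocol check for prohibited medication searches the month before Screening, so it cannot find the on-treatment use it is meant to exclude

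*SAP*

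**What the plan says.** SAP 5.3.1 tabulates the important protocol deviations that exclude a patient from PP, with one column for the deviation and one for how it is identified. In the Prohibited Medication row the deviation is: "Patients who take medications that are not permitted during the double-blind Treatment Period".

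The identification column of the same row describes a blinded review of prior and concomitant medication listings. Its instruction is "The Medical Monitor will review this list and note any prohibited medications or therapies within 1 month prior to the Screening Visit", followed by the exclusion rule: "Patients will be excluded if they had prohibited medications or therapies within 1 month prior to the Screening Visit". It contains no instruction for use on or after Day 1.

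Protocol 7.3 sets two kinds of limit for each analgesic class, a look-back before Screening and a ban during the study. Both concern drugs taken for diabetic neuropathic pain. The NSAID restriction reads, in part: "Use of NSAIDS on chronic basis within 2 weeks prior to Screening or at any time for the duration of the study for treatment of". For opioids it covers "Use of opiates in the 2 months prior to Screening or at any time for the duration of the study for treatment of DPNP".

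Under SAP 7.6, efficacy is analysed on mITT and PP is supportive. SAP 7.6.1 repeats the primary MMRM on PP.

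**The concern.** The two columns of one row describe different periods. The deviation column is about what happened during treatment; the method column, which is what someone building the PP flag would follow, is about what happened before the patient was screened.

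This matters because of what PP is for here. The primary analysis keeps all observed data, including data after rescue. The supplementary MMRM in SAP 7.6.3 removes only data after rescue medication, which is acetaminophen. PP is therefore the only planned analysis of the primary endpoint whose rules name prohibited medication. SAP 5.3.1 justifies its exclusions by their possible influence on that endpoint. If the check misses on-treatment use, the PP result can be presented as free of a confounder that is still in it. The ambiguity also means that two people working from this row could build two different PP populations.

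**Working it through.** The plan gives no figure to reproduce. The check compares time windows in study days.

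**Inputs**
- Screening target Day -28, Run-in Day -14, Week 6 visit target Day 43 (SAP Table 1.2).
- PP look-back: 1 month before Screening (SAP 5.3.1).
- Protocol look-backs: NSAIDs 2 weeks, opioids for neuropathic pain 2 months; both also barred throughout the study (Protocol 7.3).
- Assumption: 1 month = 30 days and 2 months = 60 days.

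**Step 1: overlap with double-blind treatment.** The look-back is the 30 days before Day -28, that is Days -58 to -29. Double-blind treatment is Days 1 to 43. Overlap = 0 days. If Screening fell as late as Day -14, the look-back would be Days -44 to -15 and the overlap would still be 0. The result does not depend on the length of a month: the window ends at Screening, and the 2-week Run-in lies between Screening and Day 1.

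**Step 2: against the NSAID look-back.** The protocol window is 14 days, Days -42 to -29. The SAP window is 30 days. Days searched by the SAP but outside the protocol restriction: 30 - 14 = 16. Use on those days, roughly 2 to 4 weeks before Screening, did not breach the NSAID rule.

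**Step 3: against the opioid look-back.** The protocol window is 60 days, Days -88 to -29. Days inside the protocol restriction but not searched: 60 - 30 = 30. Use on those days did breach the opioid rule, and the SAP check does not reach it.

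**Step 4: whether the right check is feasible.** SAP 7.4.2 already plans a separate summary of prohibited concomitant medication taken during double-blind treatment, so the data exist. Opioid history is different: Protocol 7.2.1 records prior medication for only 30 days before Screening, so a 2-month look-back cannot be read from the medication listings.

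**Step 5: scale, as an illustration only.** The documents give neither a rate of prohibited use nor an analgesic effect. If a fraction p of one arm uses a drug that lowers pain by b points and stays in PP, that arm's mean moves by p × b. Assuming p = 5%, b = 1.5 and use in placebo only, the shift is 0.05 × 1.5 = 0.075 points, or 7.5% of the 1-point target difference. With the plan's SD of 2 and 75 patients per group, the standard error of a treatment difference is 2 × √(2/75) = 0.327, so the shift is 0.075 / 0.327 = 0.23 standard errors. It falls to 0 if the other reviews remove every such patient or if use has the same effect in both arms, and it scales in proportion to p and b.

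**The case against.** The strongest reply is that the row's deviation column already says on-treatment users are excluded, so the method column is only loose drafting. The Medical Monitor receives concomitant as well as prior medications and could be expected to flag both. SAP 5.3.1 adds further safeguards: a row based on the clinical trial management system's deviation list, sponsor review of all important deviations during the study, and the option to add unanticipated exclusions before unblinding. All of this stands. A reader might infer from the method column that on-treatment users will stay in PP; the documents support only that they can. Equally, the safeguards do not repair the row. The deviation-list row names no medication criterion, and a named, prespecified check should not depend on a general review to do its work.

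Two further inferences go too far.
- That one month corresponds to nothing in the protocol. Section 7.3 uses one month for stable neuropathic-pain medication, for cannabidiol withdrawal and for brief opioid use for other acute pain. What is true is that one month fits neither the NSAID nor the opioid-for-neuropathic-pain look-back, and has no bearing on the on-study ban.
- That eligible NSAID users will be removed. This follows only if prohibited means the drug class. If it means use that broke Section 7.3, NSAID use 2 to 4 weeks before Screening would not be flagged.

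Two neighbouring items do not belong to this point. Excluding patients randomised in the wrong stratum is a prespecified choice on which statisticians may differ. The medication recording periods in Protocol 7.2.1 (30 days) and Appendix A footnote f (2 weeks) differ, but that is a data-collection matter and does not bear on this exclusion rule.

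**Conclusion.** Wrong as written. The Prohibited Medication row contradicts itself: its stated method and exclusion rule have no overlap with the period in which the deviation occurs, so the named check cannot detect it. The zero overlap holds for any Screening date the design allows.

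Two consequences are possible rather than certain. On-treatment users of prohibited analgesics can remain in PP unless the general deviation review finds them. Patients with NSAID use 2 to 4 weeks before Screening can be dropped if prohibited is read as the drug class.

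The size of any effect on the PP estimate is unknown. The 0.075-point figure rests on assumed inputs and is small against the standard error. A reader might infer that the trial's main result is at risk; it is not, because the primary analysis is on mITT and does not use this rule. What is at stake is whether the PP analysis supports what it claims to support.

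**What to change.** Before unblinding, rewrite the identification column of the row as a blinded review of concomitant medications taken from the first double-blind dose (Day 1) through the Week 6 assessment, judged against Protocol 7.3, with exclusion on that basis. Remove the one-month pre-Screening wording from this row.

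If pre-Screening use is also meant to exclude patients from PP, list it as a separate entry-criteria item using the protocol's own look-back periods, and take opioid history from the eligibility data because the medication listings reach back only 30 days. This would be a real addition: the current entry-criteria row covers Inclusion Criterion 9 only.

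The main change costs a few lines of SAP text, since the listings and the on-treatment summary are already planned. The optional item costs one further check of eligibility records.
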